Date: 4/14/16

Principal Investigator: [name]

Application Number: IRB0007923

NCT: 02674477

Title: Treatment Engagement With Technology-assisted Treatment

1. Abstract

Technology-assisted treatment, or TAT (e.g., online modules, mobile applications), shows promise for innovative assessment, prevention, and treatment of substance use disorders (SUDs). The widespread access to TAT makes it a potentially cost-effective and innovative option available for delivery in multiple settings. To date, there have been no published studies that investigate whether TAT is effective in patients with SUDs in addition to another psychiatric illness (dual diagnosis patients). Thus, we plan to pilot a computerized cognitive behavioral therapy (CBT) program called the Therapeutic Education System (TES) in dually diagnosed inpatients and allow them access to the program as outpatients as well. Our hypothesis is that those assigned to TES will have better program retention and outpatient attendance than those assigned to treatment as usual (TAU), because the patients using TES may be more engaged in the process of problem recognition and problem solving with regard to their mental health and substance use problems. This research will be valuable to better understand the treatment needs of this dually diagnosed population, including ways to keep them engaged in care.

2. Objectives

We propose to conduct a controlled study assessing: 1) whether exposure to TES during hospitalization is acceptable to dually-diagnosed patients, and 2) whether TES use affects post-discharge treatment retention.

3. Background

Several computerized contingency management and cognitive-behavioral interventions for SUDs have shown efficacy in single-site clinical trials, and TES has been shown to have efficacy in a clinical trial involving multiple community-based addiction treatment programs¹⁻⁴. We surveyed inpatients on two hospital-based dual diagnosis units at the Johns Hopkins Hospital (JHH) to assess their interest in, access to, and experience with TAT, as well as preferences for content and implementation. Preliminary data suggest that despite most patients having no previous TAT exposure, they would welcome TAT during and after hospitalization, and would consider it helpful. Some patients preferred face-to-face therapy alone, suggesting that TAT should not completely replace these services.

4. Study Procedures

a. Study design, including the sequence and timing of study procedures

This project will be conducted on the Motivated Behaviors Unit (MBU), which is an inpatient dual diagnosis treatment service located on Meyer 3. Standard MBU treatment comprises a psychiatrist-led interdisciplinary team as well as face-to-face group counseling for substance use and skills for improving general mental health. There will be no change to the routine care (treatment at usual [TAU]) provided to patients on the service.

Informed consent will be obtained from each potential participant. This process will include permission to contact participants following discharge, and to review their hospital chart for necessary information such as demographics and diagnoses. Volunteers will then undergo a baseline assessment on acceptability of TAT, using an instrument developed for this project, as well as an assessment of self-efficacy and health-related quality of life using the NIH Toolbox Self-Efficacy Survey⁵, and the Medical Outcomes Study 36-item Short-Form Health Survey (SF-36),⁶ respectively. Study participants will be randomized using an urn design method to receive either TAU or TAU plus TES. Patients will be stratified based on ethnicity, gender and whether

the primary drug of use is an opioid. Patients in the TES group will be taught how to use the web-based therapy while inpatient and provided access to the system while residing on Meyer 3 using a participant-specific username and password. Each person's account will be logged out at the end of their session on Meyer 3, and the laptops will not be used by other (non-study) patients, ensuring confidentiality. Participants will be encouraged to continue using the TES program after discharge by accessing the website with their login information. A reminder will be sent to them regularly via email or text message regarding their access to the program. They will be advised to log out after every session and close their browser, but to be aware that if someone were to track the history of the Internet browser, the HealthSim website would appear. Patients will be given a list of places available to use a computer for free, such as patient resource centers at JHH and the University of Maryland Hospital, as well as public libraries. The study team will have separate, password-protected access to user data within the TES program, though any patient identifiers will be kept separate from the program. HealthSim keeps user data confidential, and uses data at the minimum required for maintenance and support of the program's use by each site. Per HealthSim, "any such use, however, shall be conducted in accordance with all applicable law and regulations, including privacy regulations."

The TES program consists of a series of 65 interactive modules on substance use-related topics (e.g., effective problem solving; HIV and AIDS; drug refusal skills training). We expect it will take less than thirty minutes to complete each module. Patients will be able to access the program during 1-hour long sessions, as often as possible. We anticipate TES usage will amount to at least 2 hours per week. The assessment of TAT acceptability, self-efficacy and health-related quality of life will be re-administered prior to inpatient discharge, and then during follow up (as described below).

Many patients discharged from the MBU receive referral appointments to the Community Psychiatry Programs (CPPs) at JHH or Johns Hopkins Bayview Medical Center (JHBM) for psychiatric care, and many also go to the Broadway Center (the primary outpatient site operated by JHH for substance use treatment). When possible and appropriate, these will be the preferred referral sites for study participants, as is current practice. Patient involvement with outpatient care (i.e. enrollment) at either CPP can be tracked via the Electronic Medical Record. We will also track patient retention at other mental health and substance use treatment programs that patients may be referred to, by contacting the program directly with the patient's consent.

b. Study duration and number of study visits required of research participants.

At the time of study enrollment and prior to discharge from the hospital, patients in both groups will be administered a survey that assesses acceptability of their inpatient and outpatient treatment, self-efficacy and health-related quality of life, drug and/or alcohol relapse, and the experimental group will also be assessed for their acceptability of TES.

Since the length of inpatient stay and other factors may vary across patients, we will not attempt to dictate the number of TES modules that should be completed but will attempt to ensure that all TES participants have experience with the program before they leave and will track and record the amount of usage during the inpatient stay.

c. Blinding, including justification for blinding or not blinding the trial, if applicable.

Blinding is not possible as those getting the intervention will be using the computer program whereas those that are in the control group will not.

- d. Justification of why participants will not receive routine care or will have current therapy stopped.

All patients will receive treatment as usual, so no routine care will be stopped.

- e. Justification for inclusion of a placebo or non-treatment group.

The TAU group will not receive the TES intervention, though they will still receive the typical treatment on the unit. A comparison of the survey responses and post-discharge program adherence of the TES and TAU groups will provide information as to whether the TES intervention is helpful.

- f. Definition of treatment failure or participant removal criteria.

Participants will not be removed for treatment failure, as part of our goal is to investigate whether the TES program is easy to use by, and interesting to patients as part of the acceptability survey and review of module completion. Participants will be removed from the study if they no longer meet the inclusion criteria. For example, if a patient's status changes to involuntary they will be removed from further participation, but any data gathered up until that point will be used in analysis.

- g. Description of what happens to participants receiving therapy when study ends or if a participant's participation in the study ends prematurely.

Participants in the TES group will no longer have access to the computer-based program after the study ends, or if their participation ends prematurely, but all patients will receive standard inpatient care and referral to post-discharge treatment.

5. Inclusion/Exclusion Criteria

Potential participants will be patients voluntarily admitted to the JHH Motivated Behaviors Unit (MBU), whose patients primarily present from the East Baltimore community. Eligibility criteria include self-report of drug or alcohol use in the 30 days prior to admission, diagnosis of both a substance use disorder and other psychiatric illness, a proficiency in English, and an ability to provide informed consent. Patients who are actively psychotic, or cognitively impaired with a Mini-Mental State Examination (MMSE) score of 25 or less will be excluded. After listening to a recording of the content of the informed consent form, participants must be able to obtain a score of 100% on a consent quiz after up to 3 attempts, with a chance for remediation between attempts. We will consent 150 participants with a plan to accrue about 130 persons in order to allow for drop outs or other early removals from the study and have a total of at least 100 participants. Our screening process will involve a study team member using the electronic medical record to ensure that the patient does indeed meet criteria for inclusion. The potential participant must be willing to participate and agree to the procedures in the consent form, such as allowing the team to contact his/her post-discharge provider(s). The person should also be willing to complete the risk assessment module through the TES program and at least one other TES module if randomized to that treatment arm, and to seek post-discharge treatment. Patients must have an email address, and if they do not have one they will be assisted in setting up an email account for distribution of surveys post-discharge. If a person does not set up an email account, surveys can be administered by phone post-discharge. The preferred method of payment for participant incentives will be Bank of America prepaid debit cards, so that

funds can be electronically deposited after they are discharged from the hospital. Participants will be required to sign an agreement regarding use of these cards. If necessary in certain cases, participants may receive other physical or electronic gift cards.

6. Drugs/ Substances/ Devices

- a. The rationale for choosing the drug and dose or for choosing the device to be used.

As noted above, TES has shown efficacy in clinical trials among patients with SUDs in community-based addiction treatment programs. The two-group randomized design with TAU as the comparison condition was selected to provide a clinically relevant evaluation of TES when used as a supplement to TAU. Since acceptability and effects on post-discharge follow up care are of primary interest in this pilot trial rather than mental health or drug use outcomes, any imbalance in amount of therapy delivered should not be relevant.

- b. Justification and safety information if FDA approved drugs will be administered for non-FDA approved indications or if doses or routes of administration or participant populations are changed.

N/A

- c. Justification and safety information if non-FDA approved drugs without an IND will be administered.

The Therapeutic Education System (TES) is not a physical/mechanical device; but it is a software program that is accessed through the Internet on any PC or Mac computer using a specific username and password. Our research subjects will use it through a site-specific license, so that their information is separate from other TES users. TES does not pose any significant risk to subjects as it is not an implant, is not used for sustaining human life, does not present potential for serious risk to the health, safety or welfare of a subject and will not be used substantially in diagnosing, curing, or mitigating disease. It is a treatment, but it is not the primary treatment modality that will be employed with patients who enroll in this pilot study. As therapy, it will only be used adjunctively to treatment as usual in the form of education, in a supervised manner. Thus, TES does not meet the definition for a significant risk device, but is a nonsignificant risk device.

7. Study Statistics

- a. Primary outcome variable.

Acceptability of TES, via both self-report and actual usage, will constitute the primary outcome measure for the randomized design portion of the study.

- b. Secondary outcome variables.

The enrollment rate for outpatient mental health and substance abuse treatment at 30 days post-discharge, and patient satisfaction regarding the hospital stay among both groups will be investigated as secondary outcomes.

- c. Statistical plan including sample size justification and interim data analysis.

TES acceptability will be rated on a scale of 0-10, and will be analyzed by mean and SEM. Comparison of hospital ratings will be performed using a paired t-test. The hypothesis is that the TES group will have significantly higher ratings than the TAU group. Based on a previous study of acceptability of TES compared to standard treatment⁷, a power analysis with alpha = 0.05

indicates that 50 persons per group is adequate to demonstrate an effect size of 0.313, where estimated power is 0.87.

d. Early stopping rules.

Those patients who leave against medical advice without a follow up appointment will be excluded from further participation in the study and thus can be included in analysis of any surveys completed during their stay, but not the post-discharge surveys. Any participants who no longer meet inclusion/exclusion criteria (e.g. MMSE score falls to 25 or below) will be removed from the study.

8. Risks

a. Medical risks, listing all procedures, their major and minor risks and expected frequency.

N/A

b. Steps taken to minimize the risks.

N/A

c. Plan for reporting unanticipated problems or study deviations.

These will be reported promptly to the IRB if any arise, though this is unexpected.

d. Legal risks such as the risks that would be associated with breach of confidentiality.

Given the content of the questionnaires there is little anticipated legal risk.

e. Financial risks to the participants.

N/A

9. Benefits

a. Description of the probable benefits for the participant and for society.

The participants in the TES group will benefit from participating in this study through increasing the skill set needed to work in recovery. Patients such as those participating in this study who have a substance use disorder as well as another psychiatric illness will benefit from the findings of this study as it will help us to better understand the needs of this population and whether this treatment will help them to be more engaged in their recovery. Similarly, this research will help the field and society through advancing what is currently known about psychiatric services for treating dually diagnosed patients, and thus working to reduce the mental and physical health complications, financial burden and disability caused by addiction in the community.

10. Payment and Remuneration

a. Detail compensation for participants including possible total compensation, proposed bonus, and any proposed reductions or penalties for not completing the protocol.

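### The three factors used to balance the randomisation enter no analysis named in Section 7.c; adjusting for them costs almost nothing and recovers some power if they predict the outcome

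*Combined protocol and SAP*

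**What the plan says.** Section 4.a: "Study participants will be randomized using an urn design method to receive either TAU or TAU plus TES". The balancing factors follow: "Patients will be stratified based on ethnicity, gender and whether" "the primary drug of use is an opioid". The documents do not give the ethnicity categories, or say whether the urn runs within each combination of factors or on each factor separately.

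Section 7.c is the whole statistical plan. The 0-10 acceptability rating is summarised by mean and standard error. One test is named: "Comparison of hospital ratings will be performed using a paired t-test". The next sentence gives a between-arm hypothesis: "The hypothesis is that the TES group will have significantly higher ratings than the TAU group". What is paired is not defined. No covariate, stratified test or balancing factor is mentioned.

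Section 7.a sets the primary outcome: "Acceptability of TES, via both self-report and actual usage, will constitute the primary outcome measure for the randomized design portion of the study". Section 7.b adds enrollment in outpatient treatment at 30 days after discharge and satisfaction with the hospital stay, in both groups. Section 7.c names no test for enrollment. Section 4.e says that survey responses and post-discharge adherence will be compared between the groups.

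**The concern.** Balancing the arms on a factor that predicts the outcome makes the true arm difference vary less from one randomisation to the next. An unadjusted two-sample comparison does not see this, because the variation due to the factor stays in its error term. The reported standard error is then larger than the real one, the p-value is conservative and the interval too wide. Chance imbalance left by the urn, or created by dropout between about 130 accrued and 100 analysed (Section 5), also goes uncorrected.

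At stake is efficiency in a small trial. Because the trial is unblinded, there is also some value in fixing the covariates before data are seen, so that the model is not chosen afterwards.

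**Working it through.** **Inputs from the documents (Section 7.c).** 50 per group, alpha 0.05, effect size 0.313, power 0.87. Sidedness and the type of effect size are not stated.

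**Assumptions.** Two-sided test. R2, the share of outcome variance that the three factors explain together, is not in the documents and is taken as 0, 0.10, 0.20 and 0.30. The factors are treated as binary, with prevalences 0.5, 0.4 and 0.5.

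**Step 1: the plan's own figure.** In SD units, the standard error of an arm difference with 50 per group is sqrt(2/50) = 0.200.
- 0.313 as a standardised mean difference d: 0.313/0.200 = 1.565, power 0.34. This does not match.
- 0.313 as Cohen's f, so d = 2 x 0.313 = 0.626: 0.626/0.200 = 3.13, power 0.873. This matches.
- A paired test with 100 pairs: 0.313 x sqrt(100) = 3.13, power 0.873. This also matches, but no such pairs are defined. With 50 pairs the power is 0.58.

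The independent-groups reading that matches, d = 0.626, is used below.

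**Step 2: the limit under exact balance.** Overstatement of the standard error is 1/sqrt(1-R2). The true size of the nominal 5% test is 2 x (1 - Phi(1.96/sqrt(1-R2))).
- R2 = 0.10: 1/sqrt(0.90) = 1.05, size 3.9%
- R2 = 0.20: 1/sqrt(0.80) = 1.12, size 2.8%
- R2 = 0.30: 1/sqrt(0.70) = 1.20, size 1.9%

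An urn does not balance exactly, so these are limits and not estimates for this trial.

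**Step 3: an urn.** Simulation with 100 patients, an urn within the eight factor combinations and 4,000 runs per setting. It compares an unadjusted independent t-test with a linear model containing arm and the three factors.

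| R2 | Reported SE, unadjusted | True SE, unadjusted | Size, unadjusted | Power, unadjusted | Power, adjusted |
|---|---|---|---|---|---|
| 0 | 0.200 | 0.200 | 4.9% | 0.874 | 0.869 |
| 0.10 | 0.200 | 0.190-0.196 | 4.6% | 0.887 | 0.908 |
| 0.20 | 0.200 | 0.183-0.186 | 3.0% | 0.889 | 0.930 |
| 0.30 | 0.200 | 0.181 | 3.5% | 0.898 | 0.958 |

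The relative Monte Carlo error of each true SE is about 1/sqrt(2 x 4,000) = 1.1%. Further simulations with urns of both kinds, within combinations and on each factor separately, put the overstatement at roughly 3-4%, 5-11% and 9-10% for R2 of 0.10, 0.20 and 0.30. Power, unadjusted against adjusted, was 0.88-0.89 against 0.90-0.91, 0.88 against 0.93-0.94, and 0.88-0.89 against 0.95-0.96. The gain is about 2, 5 and 6-7 points.

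**Step 4: if 0.313 is d itself.** Simulated power, unadjusted against adjusted, is 0.336 against 0.362, 0.326 against 0.408, and 0.320 against 0.446. The gain is about 3, 8 and 13 points, from a much lower base.

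**Step 5: what R2 might mean for enrollment.** Suppose 70% of opioid patients and 40% of others enroll, in equal numbers (assumed). Then R2 = ((0.70 - 0.40)/2)^2 / (0.55 x 0.45) = 0.0225/0.2475 = 0.09, near the lowest non-zero row above.

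**The case against.** The strongest case against is that this is an efficiency preference of unknown size in a self-described pilot. Much of it stands.

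- **No loss is shown.** A reader might infer that the standard error is too large and power is being lost. The documents give no relation between the factors and any outcome. At R2 = 0 the unadjusted error is correct and adjustment gains nothing.
- **The planned power is not missed.** On the reading that reproduces 0.87, unadjusted power is 0.87 to 0.90 throughout. The error is conservative, so it produces no excess of false positives.
- **The exact-balance figures are too strong.** Overstatement of 12% or 20% and a test size of 2.8% or 1.9% do not describe an urn.
- **Not every t-test is affected.** The plan names a paired test. Pairing within patient would cancel constant factor effects but would not compare the arms. Pairs matched on the factors would already use them in part. The mismatch between a paired test and a between-arm hypothesis, and the undefined effect size, are larger problems and come first.
- **Enrollment has no stated test.** There is no specified standard error to be too large. What is missing is the analysis itself.
- **Much of the primary outcome is out of reach.** Under Section 4.b only the experimental group rates acceptability of TES, and only that group has TES usage. Neither has a control-arm counterpart.

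None of this removes the point. Replacing the paired test by a plain independent t-test would still leave the three factors unused. Choosing them for the randomisation suggests that they were thought to matter.

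**Conclusion.** The concern holds as a conditional one. The urn balances on three factors, and nothing in Section 7.c uses them. If they predict an outcome compared between arms, an unadjusted test is conservative. At an assumed R2 of 0.10 to 0.30 and d = 0.626, adjustment is worth about 2 to 7 points of power, and the unadjusted 5% test runs at roughly 3% to 4.6%. If they do not predict it, adjustment costs about half a point (0.874 against 0.869). This asymmetry is the reason to adjust, since the gain may be modest or nil but the price is close to zero.

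The size rests on three things that the documents do not give: R2, the meaning of 0.313, and the form of the urn. The documents do not support reading this as inflated type I error, as a shortfall against the stated 0.87, or as a flaw in TES-only acceptability or usage.

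**What to change.** In Section 7.c, for each outcome measured in both arms (ratings collected in both arms, satisfaction with the hospital stay, 30-day enrollment), prespecify an independent-groups model with arm and the three urn factors as main effects, in the same categories as the urn:

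- 0-10 ratings: linear regression, reporting the adjusted mean difference with a 95% confidence interval.
- 30-day enrollment: logistic regression, reporting a standardised risk difference with a 95% confidence interval.
- The unadjusted comparison as a sensitivity analysis.

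This wording also replaces the paired test for the between-arm hypothesis. Section 4.a should state the ethnicity categories and how the urn is run, so that the model can match it. TES-only acceptability and usage stay descriptive.

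The cost is one or two sentences in Section 7.c. The factors are already recorded for randomisation. The model uses three degrees of freedom out of about 98 if ethnicity is binary, and more otherwise.

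### Between-arm comparison of pre-discharge ratings is planned with a paired t-test and no baseline covariate, although both arms give the same ratings at enrolment

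*Combined protocol and SAP*

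**What the plan says.** **Measurement.** Section 4.a puts the enrolment measurement before it describes randomisation: "Volunteers will then undergo a baseline assessment on acceptability of TAT", together with self-efficacy and SF-36. The same section then says: "The assessment of TAT acceptability, self-efficacy and health-related quality of life will be re-administered prior to inpatient discharge", and again at follow-up. Nothing there limits the repeat to one arm. Section 4.b covers both arms explicitly: "At the time of study enrollment and prior to discharge from the hospital, patients in both groups will be administered a survey that assesses acceptability". What is rated there is the patient's own treatment, with self-efficacy and quality of life alongside. Only the experimental group also rates TES itself.

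**Intended comparison.** Section 4.e relies on comparing survey responses between the TES and TAU groups to judge whether TES helps. Section 7.c states the direction: "The hypothesis is that the TES group will have significantly higher ratings than the TAU group".

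**Analysis.** Section 7.c gives two analysis statements: "TES acceptability will be rated on a scale of 0-10, and will be analyzed by mean and SEM" and "Comparison of hospital ratings will be performed using a paired t-test". It does not say what is paired, and it names no covariate. The sample size rests on "a power analysis with alpha = 0.05", which "indicates that 50 persons per group is adequate to demonstrate an effect size of 0.313, where estimated power is 0.87".

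**Outcome status.** Section 7.a makes acceptability of TES (self-report and usage) primary. Section 7.b lists 30-day outpatient enrolment and satisfaction with the hospital stay. Neither lists self-efficacy or SF-36.

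**The concern.** The trial collects a pre-exposure value of several ratings in every participant and repeats the same ratings before discharge, yet the statistical plan gives that value no defined role. The only named test does not fit the stated hypothesis: TES and TAU patients are different people, so there are no pairs across arms. Whoever runs the analysis will have to replace the test.

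Two obvious replacements are wasteful. An unadjusted comparison of discharge ratings leaves stable differences between patients, such as general attitude to technology, in the error term. A comparison of change scores subtracts the enrolment value in full and so adds its noise. With about 50 per arm, the confidence interval would be wider than the collected data allow. Leaving the choice open also permits it to be made after the results are seen.

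**Working it through.** **Inputs from 7.c.** n = 50 per group, effect size 0.313 (metric not stated), alpha 0.05 (sidedness not stated; two-sided used here unless noted), power 0.87. **Assumed:** the enrolment-to-discharge correlation r, which the documents do not give.

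**Step 1. Reproduce the stated power** (noncentral t).

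- 0.313 as Cohen's d, two arms of 50: noncentrality 0.313 × √(50/2) = 1.565; power 0.34 (one-sided 0.46). Not 0.87.
- 0.313 as Cohen's f, two arms of 50: d = 2 × 0.313 = 0.626; noncentrality 0.626 × √25 = 3.13; power 0.873. Matches.
- Paired test, 50 pairs: 0.313 × √50 = 2.213; power 0.58 (one-sided 0.70). Not 0.87.
- Paired test, 100 pairs: 0.313 × √100 = 3.13; power 0.873. Matches, but it pools both arms in a within-patient test and so does not compare them.

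For a between-arm comparison, 0.87 is therefore right only if 0.313 is f. Both metrics are carried forward.

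**Step 2. Variance under each analysis**, relative to discharge ratings alone (equal variance at both times, common slope):

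- ANCOVA: 1 − r²
- Change score: 2(1 − r)
- Ratio of ANCOVA to change score: (1 + r)/2, which is below 1 whenever r is below 1

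**Step 3. Power with ANCOVA**, 50 per arm. Noncentrality is d × √25 / √(1 − r²), with 2 × 50 − 3 = 97 degrees of freedom. Example at r = 0.5: 3.13/√0.75 = 3.61 for d = 0.626, and 1.565/√0.75 = 1.81 for d = 0.313.

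| r (assumed) | ANCOVA variance | Change-score variance | Ratio | Power if 0.313 is f (d = 0.626) | Power if 0.313 is d |
|---|---|---|---|---|---|
| 0 | 1.00 | 2.0 | 0.50 | 0.87 | 0.34 |
| 0.1 | 0.99 | 1.8 | 0.55 | 0.88 | 0.34 |
| 0.3 | 0.91 | 1.4 | 0.65 | 0.90 | 0.37 |
| 0.5 | 0.75 | 1.0 | 0.75 | 0.95 | 0.43 |
| 0.6 | 0.64 | 0.8 | 0.80 | 0.97 | 0.49 |

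The variance reduction at r = 0.3, 0.5 and 0.6 is worth 1/0.91, 1/0.75 and 1/0.64, that is 10%, 33% and 56% more patients in an unadjusted comparison. A change score at r = 0.3 would lower power to 0.75 (d = 0.626) or 0.26 (d = 0.313).

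**Step 4. Can adjustment repair the sample size if 0.313 is d?** Unadjusted, power 0.87 needs 195 per arm. Reaching it with 50 requires 1 − r² = 50/195, so r = √(1 − 0.256) = 0.86.

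**Step 5. Which outcomes have an enrolment value?**

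| Outcome | Same value at enrolment, both arms? |
|---|---|
| TAT acceptability | Yes |
| Acceptability of own inpatient treatment | Yes, after little exposure to the unit |
| Self-efficacy, SF-36 | Yes, but not listed in 7.a or 7.b |
| TES acceptability | No; rated only in the TES arm |
| TES usage | No |
| 30-day outpatient enrolment | No |

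**The case against.** The strongest reply is that the outcomes that matter most are untouched. A reader might infer that the primary outcome is being analysed inefficiently. The documents do not support that: nobody has used TES at enrolment, only the TES arm rates it, and neither usage nor 30-day enrolment has a baseline. This stands in full and limits the point to ratings collected in both arms.

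Second, self-efficacy and SF-36 are not named outcomes and 7.c plans no test of them, so it would be wrong to say that a planned analysis loses precision there. This also stands. Section 4.e nevertheless intends a comparison of survey responses and gives no method, so the sentence that supplies one should supply an efficient one and mark those comparisons exploratory.

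Third, the paired test might mean discharge against enrolment within patient, in which case the enrolment value is used. The text does not say. If it is meant, a within-patient test still does not address a hypothesis about two arms, and a between-arm comparison of those differences is less precise than ANCOVA.

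Fourth, a reader might infer that chance imbalance at baseline biases the comparison. It does not. Under randomisation the unadjusted difference is unbiased, and its standard error already reflects such imbalance.

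Finally, every r is assumed, the TAT instrument was developed for this project, and the power figures apply to a generic rating. All true. The direction does not depend on r, apart from one degree of freedom; the size does.

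**Conclusion.** The point holds for between-arm comparisons of pre-discharge ratings that both arms also give at enrolment. Section 7.c names a test that cannot make the comparison and gives the enrolment value no role as a covariate. Baseline-adjusted ANCOVA answers the stated question and lowers variance by 9%, 25% or 36% at assumed r of 0.3, 0.5 or 0.6.

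How much that matters depends on the undefined 0.313. If it is f, the between-arm comparison has adequate power already and adjustment adds a margin (0.87 to 0.90–0.97). If it is d, adjustment helps (0.34 to 0.37–0.49) but does not rescue the design; a reader should not infer that it could, since that would need r of about 0.86. The gain may be small for the rating of inpatient treatment, because patients have seen little of the unit when they first give it.

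This is an improvement in precision and a correction of the test for a subset of measures in a pilot. It is not a finding of bias and not a defect in the analysis of TES acceptability, TES usage or 30-day enrolment.

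**What to change.** In 7.c, replace the paired t-test for between-arm comparisons. State that each pre-discharge rating collected in both groups (TAT acceptability, acceptability of own inpatient treatment, self-efficacy, SF-36) will be compared by ANCOVA, with the participant's enrolment value of the same rating as covariate, and that the adjusted TES-minus-TAU difference will be reported with its 95% CI. The stratification factors (ethnicity, gender, opioid as primary drug) may be added to the model.

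In the same place:

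- label the self-efficacy and SF-36 comparisons exploratory;
- state the status of TAT acceptability, which 7.a and 7.b do not list separately;
- say how a missing enrolment value is handled;
- state that TES acceptability, TES usage and 30-day enrolment are outside this model because they have no enrolment value.

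The cost is a few sentences and one degree of freedom per model for the baseline covariate, plus those for any stratification factors. No new data are collected and participants carry no extra burden.
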